#### (4) **Hour 3**

- a. Cardiac index (L/min/m^2)
- b. RAP (mmHg)
- c. PASP (mmHg)
- d. mPA (mmHg)
- e. PADP (mmHg)
- f. PCWP (mmHg)
- g. PAPi
- h. RSVWI (mmHg L m^-2)
- i. SVR (dynes/sec/cm^5)
- j. PVR (dynes/sec/cm^5)
- k. SBP/DBP/MAP
- l. API
- m. Standing weight
- n. Urine output
- o. Blood glucose taken from BMP
- p. HbA1c
- q. Current Vasoactive doses
- r. Renal function (serum Creatinine, serum eGFR)
- s. Total diuretic dose

(5) **Hour 27** - 2 hours after 2nd dose of SGLT2i, which will be administered 24 hours after first dose, or equivalent time period after which the dose would have been given for the No-SGLT2i arm.

- a. Cardiac index (L/min/m^2)
- b. RAP (mmHg)
- c. PASP (mmHg)
- d. mPA (mmHg)
- e. PADP (mmHg)
- f. PCWP (mmHg)
- g. PAPi
- h. RVSWI (mmHg L m^-2)
- i. SVR (dynes/sec/cm^5)
- j. PVR (dynes/sec/cm^5)
- k. SBP/DBP/MAP
- l. API
- m. Standing weight
- n. Urine output
- o. Blood glucose taken from BMP
- p. HbA1c
- q. Current Vasoactive doses
- r. Renal function (serum Creatinine, serum eGFR)
- s. Total diuretic dose

**(6) Hour 51 & Hour 75 - if vasoactives are still required and pulmonary artery catheter is still being used for routine clinical care**, we will continue SGLT2i for up to 4 doses, and the additional invasive hemodynamics repeated two hours after each dose will be collected.

- a. Cardiac index (L/min/m^2)
- b. RAP (mmHg)
- c. PASP (mmHg)
- d. mPA (mmHg)
- e. PADP (mmHg)
- f. PCWP (mmHg)
- g. PAPi
- h. RVSWI (mmHg L m^-2)
- i. SVR (dynes/sec/cm^5)
- j. PVR (dynes/sec/cm^5)
- k. SBP/DBP/MAP
- l. API
- m. Standing weight
- n. Urine output
- o. Blood glucose taken from BMP
- p. HbA1c
- q. Current Vasoactive doses
- r. Renal function (serum Creatinine, serum eGFR)
- s. Total diuretic dose

Leveled invasive hemodynamic measurements, standing weights, intake and outputs, blood glucose, blood pressure, vasoactive doses, and renal function will stop being collected for the

study after the fourth dose of SGLT2i, or equivalent timing for those randomized to the No-SGLT2i arm.

The leveled hemodynamic measurements measured via a pulmonary artery catheter at end expiration will be collected. A picture will be taken and shown to an Advanced HF attending not involved with the patient's current care and blinded to treatment for interpretation.

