The patient's participation in the study will end after completion of 4 doses of the SGLT2i or sooner if patient is transferred out of the CCU and continuous hemodynamic monitoring is discontinued, or if patient develops any of the safety end points as listed below. The physician will discuss the ongoing treatment plan with the patient at this point.

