## **Outcomes**

Primary outcome: Change in Indirect Fick cardiac index and change in PCWP

Secondary outcomes: changes in pulmonary artery pulsatility index (PAPi), Right atrial pressure (RAP), pulmonary artery systolic pressure (PASP), mean pulmonary artery pressure (mPA), pulmonary artery diastolic pressure (PADP), right ventricular stroke work index (RWSWI), systemic vascular resistance (SVR), pulmonary vascular resistance (PVR), mean arterial pressure (MAP), renal function, 24 hour urine output, changes in weight, changes in vasoactive dose, and blood glucose levels

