## **Safety End Points**

1. Need for initiation of second vasoactive medication and/or MAP < 60
2. Development of acute kidney injury, based on eGFR value < 30ml/min/1.73m^2
3. Adverse events reflecting urinary tract infection, genital infection, bone fracture, and diabetic ketoacidosis

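### A safety end point ends study participation, not only study drug, so Hour 27 CI and PCWP may be missing for reasons tied to response

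*Combined protocol and SAP*

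**What the plan says.** All references are to the combined protocol and SAP.

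- **End of participation** (paragraph just before Outcomes). Participation ends after four doses, or earlier if the patient leaves the CCU and continuous monitoring is discontinued, "or if patient develops any of the safety end points as listed below". The next sentence reads "The physician will discuss the ongoing treatment plan with the patient at this point".
- **Safety End Points.** The first is "Need for initiation of second vasoactive medication and/or MAP < 60". The second is "Development of acute kidney injury, based on eGFR value" below 30. The third is a group of adverse events: urinary tract infection, genital infection, fracture and ketoacidosis.
- **End of data collection** (after the Hour 51 and Hour 75 list). Measurements stop being collected for the "study after the fourth dose of SGLT2i, or equivalent timing for those randomized to the No-SGLT2i arm". Safety end points are not mentioned here.
- **Hour 27.** This assessment comes two hours after the second dose, "which will be administered 24 hours after first dose, or equivalent time period" in the control arm. It is the last one not conditional on continued vasoactives and catheter use.
- **Outcomes.** "Primary outcome: Change in Indirect Fick cardiac index and change in PCWP", with no time point. The secondary outcomes include "24 hour urine output".
- **Override rule** (Study Design). Patients whose assignment the physician overrides stay on study and their data are used. No matching rule covers safety end points.
- **Sample size** (Study Design). 80% power and alpha 0.05 need 16 per arm for 5 mmHg in PCWP and 18 per arm for 0.75 L/min/m² in CI; 20 per arm are planned. No SD, event rate, analysis method or missing-data method is given.

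**The concern.** Stopping a drug for safety and stopping observation are separate decisions, and the participation paragraph joins them. Two of the three triggers are haemodynamic or renal events, and the primary outcomes are haemodynamic. A second vasoactive started for worsening failure would tend to remove patients with high PCWP and low CI. Low MAP or falling eGFR after diuresis may remove patients with low PCWP. The link is weak for infection or fracture.

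A patient with an event before Hour 27 would then have no Hour 27 value and an incomplete 24-hour urine collection. If events differ between arms in frequency or cause, the patients left at Hour 27 are no longer the groups that were randomised. Even if they do not differ, values are lost from a trial that plans only two patients per arm more than the number stated for CI.

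**Working it through.** **1. Which reading is more natural.** The participation sentence speaks of the patient's part in the study, not of dosing. It puts safety end points beside CCU transfer with monitoring discontinued, after which no catheter data exist. Where the plan wants data kept after a treatment change (override), it says so. Against this, the collection text gives only the fourth-dose stop, and the participation paragraph goes on to discuss treatment. But that paragraph also ends participation sooner than the fourth dose, so the collection text does not settle the matter.

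**2. SDs implied by the plan's own figures.** None is stated, so 16 and 18 cannot be reproduced independently. Solving a two-sided t-test (sidedness assumed) at alpha 0.05 and power 80%:
- PCWP: 5 mmHg at 16 per arm gives SD 4.884 mmHg.
- CI: 0.75 L/min/m² at 18 per arm gives SD 0.780 L/min/m².

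**3. Selection bias (illustrative).** Assume no true effect, a fraction p of an arm lost, and correlation r between the event tendency and the outcome. The mean of those remaining shifts by r × SD × s(p), where s(p) = φ(z)/(1 − p) and z is the upper-p normal cut.
- s(0.10) = 0.1755/0.90 = 0.195
- s(0.20) = 0.2800/0.80 = 0.350

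With 20% versus 10% events and the same r in both arms, bias = r × SD × (0.350 − 0.195) = r × SD × 0.155. With losses of 4 and 2 patients (16 versus 18 left), the standard error is SD × √(1/16 + 1/18), which is 1.678 mmHg and 0.268 L/min/m².

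| r | PCWP, mmHg | CI, L/min/m² | Bias / SE |
|---|---|---|---|
| 0.3 | 0.23 | 0.036 | 0.14 |
| 0.5 | 0.38 | 0.060 | 0.23 |
| 0.7 | 0.53 | 0.085 | 0.32 |

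With equal rates and equal r the two shifts cancel and the bias is zero.

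**4. Opposite reasons for loss.** If one arm loses patients at +r and the other at −r, the shifts add. With 20% events in each arm, r × 4.884 × (0.350 + 0.350) gives 1.03, 1.71 and 2.39 mmHg at r = 0.3, 0.5 and 0.7. Against a standard error of 1.727 mmHg (16 versus 16), that is 0.6, 1.0 and 1.4 standard errors.

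**5. Hour 3.** With a constant event rate from the first dose at Hour 1, 20% by Hour 27 means 1 − 0.8^(2/26) = 1.7% by Hour 3, or 0.3 of 20 patients. Even opposite-sign selection at r = 0.5 to 0.7 then gives only 0.2 to 0.3 mmHg.

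**6. Power** (same SDs, two-sided t-test).

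| Values per arm | PCWP | CI |
|---|---|---|
| 20 vs 20 | 88% | 84% |
| 17 vs 20 | 85% | 81% |
| 16 vs 18 | 82% | 77% |

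**The case against.** The strongest reply is that the harm is doubly conditional: participation must include data capture, and the Hour 27 change must be the comparison of interest. The documents settle neither. The data are routine-care measurements, so recording them needs nothing further from the patient, and the only explicit stop to collection is the fourth dose. Ending follow-up at a safety event is also defensible in a small pilot, because later values mix drug and rescue effects.

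Much of this stands. If Hour 3 were primary, little would be lost. But bedside staff would still have to choose between two rules that disagree, and the 24-hour urine output needs a day of data whatever the primary time point.

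A reader might infer four stronger things that the documents do not support:

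- **A bias of 1.0 to 1.4 standard errors.** This needs 20% events in both arms, correlations of 0.5 to 0.7, and arms losing patients for opposite reasons. Nothing in the plan suggests that pattern. The triggers also include infection and fracture, and opposing triggers within one arm would partly cancel.
- **More events on dapagliflozin.** Potential Risks lists raised creatinine as a reaction but also says the class benefits renal function. Rates by arm are unknown.
- **A serious loss of power once an arm falls below 18.** Losing three patients in one arm leaves CI power at 81%.
- **Discarding of values taken before the event.** No text says this.

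**Conclusion.** The point holds as a conflict between two rules, with a plausible and avoidable source of missing data. On the more natural reading, safety events before Hour 27 remove Hour 27 CI and PCWP for reasons often linked to response, and no missing-data method covers the gap.

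The size of any bias cannot be known from the documents. Under assumed rates of 20% versus 10% and correlations of 0.3 to 0.7, it is about 0.1 to 0.3 standard errors. It is zero with equal rates and equal correlation, and larger only if the arms lose patients for opposite reasons. The power loss is modest. These figures rest on back-solved SDs, an assumed two-sided test, and assumed event rates and correlations.

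The point does not show that the trial will be biased, nor that Hour 27 must be primary. The choice of primary time point is a separate matter. The change is worth making because it is specific and cheap.

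**What to change.** Replace the safety clause in the end-of-participation paragraph with: *A safety end point may stop study drug. It does not stop collection of the scheduled Hour 3 and Hour 27 data while the pulmonary artery catheter is in place.* Make the data-collection paragraph agree, and analyse these patients in their assigned arm.

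Report for each arm:
- safety end points before Hour 27, by type;
- missing Hour 27 values;
- Hour 27 values taken off drug or on an added vasoactive.

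**Cost.** Protocol wording, with consent wording to match. Study Design describes all data points as routine care, so no study-only procedure is added while the catheter stays in. When to stop drug remains a clinical decision.

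**Downside.** Some Hour 27 values will reflect rescue treatment or no drug and may dilute or shift the effect, so lost power is not fully recovered; the per-arm counts let a reader judge this. Values after catheter removal, including after CCU transfer, stay missing.

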## **Outcomes**

Primary outcome: Change in Indirect Fick cardiac index and change in PCWP

Secondary outcomes: changes in pulmonary artery pulsatility index (PAPi), Right atrial pressure (RAP), pulmonary artery systolic pressure (PASP), mean pulmonary artery pressure (mPA), pulmonary artery diastolic pressure (PADP), right ventricular stroke work index (RWSWI), systemic vascular resistance (SVR), pulmonary vascular resistance (PVR), mean arterial pressure (MAP), renal function, 24 hour urine output, changes in weight, changes in vasoactive dose, and blood glucose levels

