### **Study Design, Study Procedures, and Statistical Procedures**

This study is designed as a single center, prospective, randomized controlled study to assess cardiac benefit of SGLT2i in 40 consecutive patients (20 treatment, 20 control) admitted to University of Chicago Cardiac Intensive Care Unit (CCU) Advanced Heart Failure Service. Patients will be randomized to one of two routine care arms: treatment with an SGLT2i (dapagliflozin 10 mg daily) or no SGLT2i. Assuming a power of 80% and alpha of 0.05, 16 patients are needed in each arm of the study to detect a 5 mmHg change in pulmonary capillary wedge pressure (PCWP), and 18 patients are needed in each arm of the study to detect a 0.75 L/min/m^2 change in Fick cardiac index (CI).

Patients  $\geq 18$  years old, with heart failure with reduced ejection fraction (HFrEF), defined as left ventricular ejection fraction (LVEF)  $\leq 40\%$ , who are admitted to the CCU for acute decompensated heart failure and determined to need pulmonary artery catheter in place for continuous hemodynamic monitoring following right heart catheterization, will be included in this study. Patients listed for cardiac transplantation or on mechanical support will be excluded. Due to the inability to consent patients following sedation given during the right heart catheterization,

patients determined to have a high likelihood of needing CCU admission, based on individual clinical presentation, will be approached for recruitment and asked for informed, written consent. However, patients will only be enrolled if it is determined independently to admit the patient to the CCU with the pulmonary artery catheter in place. If determined to need CCU care with continuous pulmonary artery catheter monitoring, patients will then be randomized, in a 1:1 fashion using the random number generation function in Microsoft Excel, to either treatment with an SGLT2i (dapagliflozin 10mg once daily) or no SGLT2i. Therefore, we anticipate recruiting and consenting more than 40 patients, but we will only randomize and treat patients that fulfill all inclusion criteria. Patients consented but not meeting randomization criteria will not have any data collected or change to their management.

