The patient's treating physician will be able to override randomization assignment if the physician determines that the assignment is not in the patient's best interest. These patients would be kept on study and their data would be used for observational research within this study.

Data points to be collected: Leveled invasive hemodynamics measured via pulmonary artery catheter at end expiration, standing weights, intake and outputs, blood glucose from basic metabolic panels (BMP) taken at those time points, HbA1C (if not within 3 months), blood pressure (cuff pressure), vasoactive doses, and renal function (measured by serum creatinine and estimated GFR) will be captured at multiple time points during CCU admission, as described below. All data points collected for use in this study are being measured as part of the patient's routine care.

**(1) Cardiac catheterization lab prior to CCU arrival:** Initial baseline hemodynamics obtained in the cardiac catheterization lab prior to CCU arrival will be collected.

- a) Cardiac index (L/min/m^2) by Indirect Fick Method
- b) Right atrial pressure (RAP) (mmHg)
- c) Pulmonary artery systolic pressure (PASP) (mmHg)
- d) Mean pulmonary artery pressure (mPA) (mmHg)
- e) Pulmonary artery diastolic pressure (PADP) (mmHg)
- f) Pulmonary capillary wedge pressure (PCWP) (mmHg)
- g) Pulmonary artery pulsatility index (PAPI)
- h) Right ventricular stroke work index (RVSWI) (mmHg L m^-2)
- i) Systemic vascular resistance (SVR) (dynes/sec/cm^5)
- j) Pulmonary vascular resistance (PVR) (dynes/sec/cm^5)
- k) Systolic, diastolic, and mean blood pressure (SBP/DBP/MAP) (mmHg)
- l) Aortic pulsatility index (API)

**(2) Hour 0 – Leveled hemodynamics,** repeated within two hours of arrival to CCU bed from cardiac catheterization lab prior to SGLT2i administration/equivalent if randomized to no SGLT2i arm, will be collected. All baseline data points to be collected at this time.

- a. Cardiac index (L/min/m^2)
- b. RAP (mmHg)
- c. PASP (mmHg)

- d. mPA (mmHg)
- e. PADP (mmHg)
- f. PCWP (mmHg)
- g. PAPi
- h. RSVWI (mmHg L m^-2)
- i. SVR (dynes/sec/cm^5)
- j. PVR (dynes/sec/cm^5)
- k. SBP/DBP/MAP
- l. API
- m. Standing weight
- n. Urine output
- o. Blood glucose taken from BMP
- p. HbA1c
- q. Current Vasoactive doses
- r. Renal function (serum Creatinine, serum eGFR)
- s. Total diuretic dose

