(3) **Hour 1** – Following repeat hemodynamics in CCU bed, patients will be given SGLT2i if randomized to SGLT2i arm, or not given SGLT2i if randomized to no SGLT2i arm.

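### Both primary outcomes are a bare change with no baseline adjustment planned; a linear model adjusted for the Hour 0 value would usually be more precise and could cost at most about 3%

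*Combined protocol and SAP*

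**What the plan says.** The Outcomes section gives the primary outcome as "Change in Indirect Fick cardiac index and change in PCWP". It does not say from which reading, to which time, or by what model.

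The Study Design, Study Procedures, and Statistical Procedures section holds the only statistical text. It sets power at 80% and alpha at 0.05, states that "16 patients are needed in each arm of the study to detect a 5 mmHg change" in PCWP, and gives 18 per arm for 0.75 L/min/m² in Fick cardiac index. The plan is 20 per arm. No test, SD, model or covariate is named, there or elsewhere.

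Two pre-dose sets of readings exist, and both are called baseline:
- Cath lab: "Initial baseline hemodynamics obtained in the cardiac catheterization lab prior to CCU arrival will be collected".
- Hour 0, in the CCU bed: "All baseline data points to be collected at this time".

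The Hour 1 item fixes the order of Hour 0 and dosing: "Following repeat hemodynamics in CCU bed, patients will be given SGLT2i if randomized to SGLT2i arm". Hour 0 is therefore the last reading before treatment, and its list of measurements matches those at Hours 3, 27, 51 and 75.

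Hours 3 and 27 carry no condition. Hours 51 and 75 are collected only "if vasoactives are still required and pulmonary artery catheter is still being used for routine clinical care".

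**The concern.** Subtracting the baseline amounts to fixing the slope of follow-up on baseline at 1. A linear model estimates that slope instead. When the true slope is below 1, as it is for equal SDs and any correlation short of perfect, subtraction over-corrects and adds noise.

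At stake is the width of the confidence intervals for the two primary comparisons in a trial of 40 patients, which the Data and Safety Monitoring section describes as the minimum needed. The covariate is already being collected, so precision would be given up for nothing.

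**Working it through.** **Inputs from the protocol.** 5 mmHg with 16 per arm (PCWP); 0.75 L/min/m² with 18 per arm (cardiac index); 80% power; alpha 0.05; 20 per arm planned.

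**Assumed, because the documents do not give them.** A two-sided two-sample test; the SDs; the correlation rho between Hour 0 and follow-up; and the SD ratio k = follow-up SD / Hour 0 SD.

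**Step 1: the plan's own figures.** Without an SD, 16 and 18 cannot be reproduced independently, so the SDs were back-solved. At 80% power the noncentral t gives 4.88 mmHg (16 per arm) and 0.78 L/min/m² (18 per arm). The normal formula gives 5.05 and 0.80. As a check with rounded SDs of 5 and 0.8, 2 × (1.96 + 0.84)² × (SD/difference)² gives 15.7 and 17.9, which round up to 16 and 18. The stated sizes are plausible but not verifiable.

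**Step 2: variances.** With Hour 0 SD = 1:
- Var(change) = 1 + k² − 2·rho·k
- Var(adjusted) = k²(1 − rho²)
- The difference is (1 − rho·k)², which is never negative and is zero only when the slope rho·k equals 1.

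**Step 3: cost of estimating the slope at N = 40.** Chance baseline imbalance multiplies the variance by 37/36 = 1.028. Residual degrees of freedom fall from 38 to 37, so critical t goes from 2.0244 to 2.0262, and (2.0262/2.0244)² = 1.002. Together these cost 1.030, or about 3% of squared confidence-interval width.

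**Step 4: net effect with equal SDs (k = 1).** The ratio simplifies to (1 + rho)/2 × 37/36. Power below uses 20 per arm and takes the back-solved SDs as SDs of change; the unadjusted figures are 88% (PCWP) and 84% (cardiac index).

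| rho | Net variance ratio | Reduction | PCWP power, adjusted | Cardiac index power, adjusted |
|---|---|---|---|---|
| 0.3 | 0.668 | 33% | 97% | 95% |
| 0.5 | 0.771 | 23% | 95% | 92% |
| 0.7 | 0.874 | 13% | 92% | 89% |
| 0.9 | 0.976 | 2% | 89% | 85% |

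Break-even, counting the lost degree of freedom, is at rho of about 0.94.

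**Step 5: unequal SDs.** Net variance ratios, including the factor 37/36:
- k = 1.5, rho = 0.3 (slope 0.45): 2.0475/2.35 × 37/36 = 0.895, a gain of about 10%.
- k = 1.5, rho = 0.9 (slope 1.35): 0.4275/0.55 × 37/36 = 0.799, a gain of about 20%.
- k = 1.25, rho = 0.8 (slope 1.00): 0.5625/0.5625 × 37/36 = 1.028, the worst case.

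A simulation of 40,000 trials with 20 per arm agrees: 0.767 against 0.771 (k = 1, rho 0.5), 0.803 against 0.799 (k = 1.5, rho 0.9) and 1.031 against 1.028 (k = 1.25, rho 0.8).

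In the worst case, power at 20 per arm would fall from 88% to 87% (PCWP) and from 84% to 83% (cardiac index).

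**The case against.** **The protocol never chooses an unadjusted change score.** This stands. No test is stated, and the word change does not rule out adjustment: regressing change on arm and baseline gives the same treatment estimate as regressing the follow-up value on them. The gains above are measured against an assumed comparator. What the documents do show is that no adjustment is planned.

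**A reader might infer bias, or an underpowered trial.** Neither is supported. A change score is unbiased under randomisation. If the back-solved SDs are SDs of change, the unadjusted analysis already has 88% and 84% power, because 20 per arm exceeds the stated 16 and 18. If they are SDs of single readings (equal SDs assumed), the change score drops below 80% only for rho under about 0.37 (PCWP) or 0.44 (cardiac index). The documents do not say which kind of SD was used.

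**A reader might infer that a larger follow-up SD cancels the gain.** It does not by itself. What matters is whether the slope is near 1 (step 5).

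**A reader might distrust Hour 0** because the treating physician is told the assignment and the protocol does not say whether that happens before or after the Hour 0 reading. The documents show no problem here: Hour 0 precedes the dose, and the tracings go to an attending outside the patient's care who is "blinded to treatment for interpretation". Switching to the cath-lab reading as baseline is not justified on this ground and could defeat the purpose. If rho were 0.7 for Hour 0 and 0.5 for the cath lab (equal SDs), the cath-lab-adjusted variance would be 0.75/0.60 × 37/36 = 1.28 times that of a plain change from Hour 0.

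**It is a pilot, and the gain may be small.** This is fair at high rho, where the gain is about 2%. The possible loss is about 3%, against a possible gain of a third at rho 0.3.

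**Conclusion.** The point holds as one of efficiency. Both primary outcomes are a bare change, no baseline adjustment is planned, and a suitable covariate is already collected before dosing. Against an assumed unadjusted change score, adjustment for Hour 0 lowers the variance by 2% to 33% for rho from 0.9 down to 0.3 with equal SDs. It has little or no benefit only where rho·k is close to 1, and it can never cost more than about 3% of squared confidence-interval width at N = 40.

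The size rests on assumed values of rho and k. The power figures rest further on a two-sided test and on reading the back-solved SDs as SDs of change. The validity of the trial is not in question. This is a change the plan should make because it is nearly free.

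**What to change.** For PCWP and Indirect Fick cardiac index separately, prespecify as the primary analysis a linear model of the value at one named follow-up time on randomised arm plus the Hour 0 value of the same measure. Report the adjusted difference with its 95% confidence interval.

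- **Baseline:** name Hour 0, since the cath-lab set is also called baseline.
- **Time point:** Hour 3 or Hour 27 would serve, as both are unconditional. Hour 27 is a suggestion only. Hours 51 and 75 depend on continued vasoactive and catheter use and are less suitable.
- **Method:** state that cardiac index at Hour 0 and at follow-up is by the Indirect Fick method. The lists of data points label it so only for the cath lab.

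The cost is a few sentences of analysis wording and, statistically, at most about 3% of squared confidence-interval width. No additional data, patients or procedures are needed.
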